5.5 STUDY DESIGN DIAGRAM

[figure not shown]

Figure 1. Study Design flow chart

5.6 STUDY TYPE & DESIGN & SCHEDULE

This project will utilise an intervention-controlled, cross-over study design with two groups (see Figure 1). It will be a single-site study, completed within Integrated and Community Health in WSLHD and will be conducted across multiple ECECs within WSLHD .

Early childhood educators from ECECs within the Cumberland City Council Local Government Area will be enrolled to participate in the Training before the commencement of the current research. The Training is a continuing service that is currently provided by the speech pathology team in Child and Family Health within WSLHD. Two training stages will be conducted in 2021 and will form Stage 1 and Stage 2 of the current study.

All educators who are enrolled to attend the Training in 2021 will be invited to participate in the current study (see [Recruitment procedure](#) for further details). Following educator consent, each consenting educator will be paired with a child who meets the study inclusion criteria (see [Inclusion Criteria](#)) and educator-child dyads will be formed. These dyads will then be randomised in to one of two groups at the ECEC level: (1) Group A will receive training in Stage 1, (2) Group B will receive training in Stage 2 (see [Fig. 1](#)). Given this research design, only Group B will have a control period (8 weeks) and only Group A will have a follow-up period (8 weeks), in which no training is provided. Educators who do not provide consent to participate in the current study will still receive the training. No data will be gathered for the purposes of this research from participants who did not provide consent.

The study population will be adult early childhood educators who are enrolled in the Training and children (aged 24-42 months) with typically developing speech and language skills in their care at an ECEC within the Cumberland City Council Local Government Area. Young children (aged 24-42

months) were selected as the population of interest for the current study due to the influence of Trained adult interaction strategies on language learning in children this age.

5.6.1 Research time frame

The timeframe for the current study will be 20 months from the time of recruitment until the end of the final stage of data collection. Data will be collected at five time points for all participant dyads: (1) recruitment and screening of participants (Time 1), (2) before Stage 1 Training (Time 2), (3) after Stage 1 Training (Time 3), (4) before Stage 2 Training (Time 4), and (5) after Stage 2 Training (Time 5) (see Table 1). Both training stages will be 8-weeks in length and there will be a five-week period between Stage 1 and Stage 2 within which Time 3 and Time 4 data will be collected from all dyads. Analysis and dissemination will continue for approximately 12 months from the completion of data collection.

Table 1. Research Time Frame

Study Time Frame	2021						2022
	Apr- Jun	Jul	Jul- Sep	Sep	Oct- Dec	Dec	Jan- Dec
Time 1: Recruitment and screening	2 mths						
Time 2: Data collection before Stage 1		1-2 wks					
Stage 1: Training implemented with Group A			8-wks				
Time 3: Data collection after Stage 1				1-2 wks			
Time 4: Data collection before Stage 2				1-2 wks			
Stage 2: Training implemented with Group B					8-wks		
Time 5: Data collection after stage 2						1-2 wks	
Data analysis and dissemination							12 mths

Time 1 will include the collection of demographic information about Educator and Child participants and confirmation of child eligibility to participate in the research. Times 2-5 are for the purpose of collecting outcome measure data. Difference scores on the primary and secondary outcome measures will be calculated between Time 2 and Time 3 (Difference Score 1, Stage 1) and Time 4 and Time 5 (Difference Score 2, Stage 2). Data for the current study will be collected from video recordings of adult-child interactions completed at Times 2, 3, 4 and 5. Data will include the extent to which the educator demonstrates interaction strategies and the language productivity and complexity demonstrated by the child in each dyad (see Table 2 for the data collection schedule). The inclusion of post-training evaluation of interactions at Time 4 and 5 is to determine the maintenance of interaction strategies demonstrated by Educators in Group A as well as any change in children’s language during a period of no active Educator training.

All analysed data will be de-identified and stored in this de-identified form for the purposes of all analysis. Only the video recordings will be identifiable for the life of the project as video samples cannot be de-identified of all identifiable information. All data, including video samples and extracted data will be re-identifiable only by a member of the research team, employed by WSLHD. It will be re-identified for limited purposes (i.e., to provide a report to the child’s family member at a future date as requested). See a detailed description of data storage protocols during and after the study period in [Section 9](#).

5.6.2 Data collection schedule

Time 1. Following Educator consent, the Educator Demographic Questionnaire (see Appendix A) will be used to collect demographic information from educators during Time 1 via a Microsoft Teams survey or as a hard-copy. This survey requests the disclosure of information related to the educator’s age, gender, country of birth, languages spoken, language proficiency, work history, and education. Following parent consent, demographic information will be gathered

for child participants during Time 1 using questions from the routine demographic questionnaire of the LHD (see Appendix B). At least two other tasks will be conducted for child participants at Time 1. Firstly, the Preschool Language Scales Screener (PLS screener; Zimmerman, Steiner, & Pond, 2011) (Appendix C), a 10-minute screener to identify possible communication impairment, will be completed with the child by a member of the research team in their ECEC, with the Speech Pathologist administering the screener via videoconference due to the impacts of the pandemic. Second, the communication section of the Ages and Stages Questionnaire (ASQ; Squires, Bricker & Twombly, 2009) (Appendix D) will be completed with the child's parent via phone. For multilingual child participants, the BabyLabs Language Exposure Questionnaire (Cattani et al., 2014) (Appendix E) will be completed with the child's parent via phone (see Table 2).

Time 2-5. Fifteen-minute interactions within each educator-child dyad will be video recorded at these four time points. These interactions will take place at the ECEC they attend. Recordings will be viewed and coded by a named member of the research team for the purpose of analysis and outcome measures will be obtained (Appendix F). All interactions will be recorded in the ECEC attended by both the educator and the child. No home visits will be required for the current study. Furthermore, each educator will complete the routine educator Training Survey before and after their training period. That is, Group A will complete the survey at Times 2 and 3 and Group B will complete the questionnaire at Times 4 and 5.

5.6.3 Data management

All participant data will be de-identified, with each participant assigned a participant number. Individual identifiable results will not be reported to participants or reported in an identifying form within published journal articles or presentations. A master document will be established to link participant numbers with identifying participant details. This document will be password protected and stored on the WSLHD server. The linking document will only be accessible by WSLHD research partners named on the project. See a detailed description of data storage protocols during and after the study period in [Section 9](#).

5.6.4 Student involvement in the project

This protocol *may* be used towards an honours student project in the future. If this change is proposed by the research team, the student will be supervised by a member of the university team and a member of the WSLHD team. An amendment to the current protocol would be submitted to the HREC for consideration in the event of student involvement in this protocol.

5.7 STANDARD CARE AND ADDITIONAL TO STANDARD CARE PROCEDURES

The data collection schedule and an indication of whether tasks are routine/standard care or additional are provided in Table 2 below.

Table 2. Data collection schedule for the current study

Entity	Data/Tool	Procedure	Time	Routine ^a or additional	Time
Educator	Consent	Returned via email	-	Additional	Before Time 1
Child	Parental consent				
Educator	Demographic information (Appendix A)	Completed online or on paper	5 mins	Additional	Time 1
Child	Demographic Information (Appendix B)		30 mins	Additional	Time 1

Child	ASQ communication section (Appendix D)	Phone call with a member of the research team			
Child	BLEQ (Appendix E) (multilingual children only)				
Child	PLS Screener (Appendix C)	Directly screened by a Speech Pathologist via videoconference at the child's centre	10 mins	Additional	Time 1
Educator	Training survey	Completed online or on paper	10 mins (x2)	Routine	Pre and post training
Educator/child dyad	Conversational interactions: analysed with Educator Interaction Strategies: Video Observation Tool (Appendix F) and conversational analysis	Video recording at the ECEC	15 mins (x4)	Additional	Time 2, 3, 4, 5

Note. ^a Routine data will be collected to support the implementation of the professional development program with all attendees. Only the data from consenting attendees will be evaluated. Additional data is data that is collected only for the purposes of this research to evaluate the feasibility of this program. None of the additional data will be collected from participants who do not provide consent. ASQ = Ages and Stages Questionnaire (ASQ; Squires, Bricker & Twombly, 2009), BLEQ = BabyLabs Language Exposure Questionnaire (BLEQ; Cattani et al., 2014), PLS = Preschool Language Scales Screener (PLS screener; Zimmerman, Steiner, & Pond, 2011).

5.8 RANDOMISATION

Centres participating in the Training will indicate availability for either or both of the training periods. We will use the random number generator at <https://www.random.org/integers/> to allocate centres who indicate availability for both stages. Therefore, pseudo-cluster randomisation will be implemented, as centres who are available in one time period only will not be randomised for pragmatic reasons. Randomisation will occur at the cluster or centre level to avoid cross-contamination effects between trained and untrained educators. This will occur after educators and children have been recruited in to the current study. This pseudo-randomization is required for the current, pragmatic study.

Masking of educators to training (+training) and no training (-training) conditions is not possible as they are actively participating in the training. The speech pathologist who analyses interaction skills will be blinded to which time point the video is recorded in and the condition that the educator is assigned to (+ training or –training). Therefore, this is a single blinded study.

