8. STATISTICAL METHODS

8.1 SAMPLE SIZE ESTIMATION, JUSTIFICATION, AND CALCULATION

The sample size will be 24 Child-Educator dyads. A target of 12 dyads will be in Group A and 12 will be in Group B. This sample size is selected as a pragmatic threshold due to the likely enrolment of 24-28 educators per training period with an approximate 50% recruitment rate. A sample size larger than 24 dyads is not feasible for the context of the current study. This calculation also allows for dropout of 10% which is consistent with previous similar investigations. This sample size is also comparable to other similar studies in early childhood education (cf McDonald et al., 2015).

Previous data with comparable outcome measures was used to estimate the intra-class correlation (ICC) in a similar setting of educators grouped by centre. For most outcome measures, the ICC was estimated to be 0.1 or lower. Assuming two educators per centre (cluster), with six centres per treatment, a standard deviation in change score of 0.3 (Piastra et al., 2012; Berry-Kravis et al., 2013), an ICC of 0.1, alpha 0.05 and power 0.8, the study should be powered to detect a difference of 0.358. This is comparable to the difference in change score of 0.4 that was previously observed (Piastra et al., 2012).

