8.2 STATISTICAL METHODS TO BE UNDERTAKEN

All questionnaire data will be collected via Microsoft Teams and exported in raw format for processing in R or SPSS. Demographic information (including age, languages spoken, language proficiency, educator level of education, educator years of experience, and child communication measures [ASQ and PLS]) will be described for all dyad participants. Two multiple linear regression analyses will be conducted to address the primary aim (Stage 1 contrast) and our secondary aim (Stage 2 contrast). The outcome (dependent variable) for both analyses will be children's mean length of utterance Difference Score across each Stage. Independent variables will be Group allocation (A or B) and cluster (ECEC). This analysis plan will allow for the primary investigation to be conducted on data collected in Stage 1. This primary analysis will investigate the impact of group allocation (Training [Group A]; Control [Group B]) and cluster (Educator Centre) on children's language output (Mean Length of Utterance). The secondary investigation will be conducted on data collected in Stage 2. This secondary analysis will investigate the impact of group allocation (No-training follow-up [Group A]; Training [Group B]) and cluster (Educator centre) on children's language output.

Intention-to-treat analysis will be completed in the event of educator drop-out from the training. If appropriate, per-protocol analysis will be completed to investigate the primary and secondary outcomes.

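### Centres available in only one stage are placed by availability but enter the primary Stage 1 contrast undistinguished from randomised centres, and the random draw is not restricted to secure the 12:12 target

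*Protocol*

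**What the plan says.** Protocol 5.6 describes the allocation without exception: "These dyads will then be randomised in to one of two groups at the ECEC level".

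Protocol 5.8 describes something narrower. "Centres participating in the Training will indicate availability for either or both of the training periods", and an online random-integer generator is used "to allocate centres who indicate availability for both stages". The remainder are handled differently: "centres who are available in one time period only will not be randomised for pragmatic reasons". The section openly names this pseudo-cluster randomisation and gives a pragmatic reason. On timing it adds: "This will occur after educators and children have been recruited in to the current study".

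Protocol 8.1 sets the size: "A target of 12 dyads will be in Group A and 12 will be in Group B". The detectable difference of 0.358 assumes six centres per group and two educators per centre.

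Protocol 8.2 gives the primary analysis as a linear regression of the difference score on group and centre. "This analysis plan will allow for the primary investigation to be conducted on data collected in Stage 1". The section has no term, stratum or restriction for how a centre came to be in its group.

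**The concern.** A one-stage centre can only be trained in the stage for which it is available, so its group follows from its availability. Whatever drives availability, such as staffing, management or workload, is then confounded with training in that centre. Such centres carry no randomised information on the training effect, yet they enter the single Group A versus Group B contrast on the same footing as the randomised ones. The protocol neither estimates nor caps their number.

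The centre term does not help. Each centre lies wholly in one group. As a fixed effect, centre is therefore collinear with group. As a random effect, it allows for correlation within a centre but not for a systematic difference between early-available and late-available centres. Allocating after recruitment protects only the both-stage centres, because a one-stage centre's group can be known before its children are recruited.

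The lesser concern is balance. The power statement rests on six centres per group, but 5.8 describes no blocking, permutation or allowance for centres already fixed in a group.

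**Working it through.** **Inputs from Protocol 8.1:** SD of change 0.3; ICC 0.1; 2 educators per centre; 6 centres (12 dyads) per group; alpha 0.05, taken as two-sided; power 0.80; stated detectable difference 0.358; previously observed difference 0.4.

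**Not in the protocol:** the number of one-stage centres, and any difference in growth between Stage-1-only and Stage-2-only centres. Both are assumed below.

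**1. The stated figure.** The design effect is 1 + (2 − 1) × 0.1 = 1.1, so the effective SD is 0.3 × √1.1 = 0.3146. By normal approximation the detectable difference is (1.960 + 0.842) × 0.3146 × √(2/12) = 0.360, and power at 0.358 is 0.796. The stated 0.358 is therefore reproduced, for a 6:6 split.

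**2. Bias from the one-stage centres.** Let f be the share of centres in each group placed by availability, taken as equal in the two groups. Let b be the difference in mean change, absent any training effect, between Stage-1-only and Stage-2-only centres. The both-stage centres are balanced in expectation, so the bias of the all-centre contrast is f × b.

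| f (assumed) | b (assumed) | Bias | As % of 0.358 |
|---|---|---|---|
| any | 0 | 0 | 0 |
| 0.25 | 0.2 | 0.05 | 14 |
| 0.50 | 0.2 | 0.10 | 28 |

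With a standard error of 0.3146 × √(2/12) = 0.128, biases of 0.05 and 0.10 would raise the two-sided type I error from 0.05 to 0.068 and 0.122. The sign of b is equally unknown.

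**3. Balance, if each both-stage centre were drawn independently with probability 1/2.** Take 12 centres in all, with some already fixed by availability. A split of 8:4 or worse means that the groups differ by at least four centres.

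| Fixed A:B | Drawn | P(6:6) | P(8:4 or worse) |
|---|---|---|---|
| 0:0 | 12 | 0.226 | 1588/4096 = 0.388 |
| 2:2 | 8 | 0.273 | 74/256 = 0.289 |
| 3:3 | 6 | 0.313 | 14/64 = 0.219 |

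If the fixed centres fall on one side, balance is worse. With four Stage-1-only centres and no Stage-2-only centres, P(6:6) is 0.109 and Group A averages 8 of 12 centres.

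**4. What imbalance costs** (normal approximation, two dyads per centre):

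| Split | Detectable difference | Power at 0.358 |
|---|---|---|
| 6:6 | 0.360 | 0.796 |
| 7:5 | 0.365 | 0.785 |
| 8:4 | 0.382 | 0.748 |
| 9:3 | 0.416 | 0.675 |

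Averaged over independent draws with no fixed centres, power at 0.358 is 0.756.

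**5. Precision with randomised centres only** (balanced, same method): 10 centres give a detectable difference of 0.394 and power 0.72 at 0.358; 8 give 0.441 and 0.62; 6 give 0.509 and 0.50.

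**6. Why an overall 6:6 should not be forced.** If four fixed centres were all Stage-1-only, an overall 6:6 would require the eight randomised centres to split 2:6, that is 4 against 12 dyads. The randomised-only detectable difference would be 2.802 × 0.3146 × √(1/4 + 1/12) = 0.51, against 2.802 × 0.3146 × √(1/8 + 1/8) = 0.44 at 4:4.

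**The case against.** Several stronger readings are tempting, and the protocol does not support them.

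- **That the result will be presented as fully randomised.** Section 5.8 discloses the non-random placement and labels it as such. Section 5.6 is an overview that omits the exception. That is a conflict to reconcile, not evidence of intended misreporting. Disclosure still does not remove the confounding from the estimate.
- **That centres will be drawn independently.** Section 5.8 names a generator, not a scheme, and integers could equally rank centres for a restricted list. What stands is that no restriction is described. The 39% figure also applies only if no centre is fixed.
- **That imbalance is a serious threat.** The 12:12 split is called a target. Section 8.1 expects 24-28 enrolled educators per training period with about 50% recruited, or 12-14 per stage, which makes extreme splits less plausible. A 7:5 split costs about one power point. This part is secondary.
- **That a material bias has been shown.** It has not. The outcome is a within-dyad difference score, so stable level differences between centres cancel and only differential growth matters. A growth difference of 0.2 is two-thirds of the stated SD and half the previously observed effect, and nothing in the protocol supports that size. Section 6.2.1 also plans a baseline comparison of educators' education, though this covers only one possible confounder.
- **That the lack of a sensitivity analysis is itself an error.** That could sit in an SAP that is not shown. What the protocol does fix is who is randomised and the primary contrast, and its own sections disagree on the first.

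**Conclusion.** The point holds in a limited form. Sections 5.6 and 5.8 contradict each other on whether all dyads are randomised. Followed as written, 8.2 yields one primary estimate that mixes a randomised contrast with one determined by availability. That the two kinds of centre are pooled is inferred from the single contrast in 8.2. The size and direction of any bias cannot be found from the protocol, and zero is possible. The range of 0 to 0.10 is illustrative, resting on an assumed share of 25-50% and an assumed growth difference of 0 to 0.2.

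The lack of a stated restriction on the draw is the smaller part. It leaves the basis of the 0.358 unsecured, at a cost of about five power points if the split came out at 8:4. Both parts should be corrected; neither makes the trial uninterpretable.

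**What to change.** 1. **Sections 5.6 and 5.8.** Correct 5.6 so that it states the exception in 5.8, and describe the all-centre estimate as partly non-randomised wherever it is reported.
2. **Section 8.2.** Prespecify the Stage 1 comparison in randomised centres only. Always report it beside the all-centre estimate, with counts of centres and dyads by allocation type. Limit any claim of a randomised effect to the randomised-centre estimate. Do not make the choice between the two depend on whether they differ, since that would be a data-dependent switch.
3. **Section 5.8.** Allocate the both-stage centres by a restricted random permutation, as near 1:1 as possible within those centres, and save the list. Do not force 6:6 overall, since that can unbalance the randomised comparison.

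The cost is wording in three sections and one extra model. The real downside is low precision in the randomised-only estimate: a detectable difference of about 0.44 (power 0.62 at 0.358) with 8 balanced centres, and about 0.51 (power 0.50) with 6. For that reason it should accompany the all-centre estimate rather than replace it.

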5.9 STUDY METHODOLOGY

As described above, the current study will include data collected at five time-points (see research time frame in Table 1). The procedures for the current study are listed in the data collection schedule in Table 2.

6. STUDY POPULATION

6.1 RECRUITMENT PROCEDURE

There will be two types of participants in the current study: Educators and Children. Once educators ($n = 24$) and eligible children ($n = 24$) are recruited, educators and children will be paired, as feasible,

by centre of attendance and language background to form dyads. The recruitment for each participant group is detailed in the sections below.

6.1.1 Educator recruitment

All educators who are enrolled to participate in Training provided by WSLHD speech pathologists will be invited to participate in the current study. All educators will be contacted via email (Appendix G) by an investigator on the research team. The email to potential participants will include the Educator Participant Information Sheet (Appendix H) and the Educator Consent Form (Appendix I). Educators who do not respond to this email will be sent a follow-up email one week later by the research team. If no response is received from an invited educator, no further contact will be made by the research team and the enrolled educator will continue in the Training without participation in the current study. If an educator responds with a signed consent form, they will be a participant of the current study and will be sent the Educator Demographic Questionnaire (at Time 1, see Appendix A). In the case of multilingual educators, all reasonable efforts will be made to match educators with child participants who are enrolled in their ECEC and share a non-English language with the Educator to allow for code-switching during interaction sessions as deemed appropriate by the Educator.

[figure not shown]

Figure 2. Educator recruitment. Relevant appendices are G, H and I.

